#### **10.4.1.4 Events of special Interest**

An EOSI is a serious or nonserious AE of scientific and medical concern specific to the Sponsor’s product or program, for which ongoing monitoring may be appropriate. Such events may require further investigation in order to characterize and understand them. These events should be reported on the specific e-CRF page (where applicable) and will only qualify for expedited reporting when serious (fulfilling SAE criteria).

The EOSIs for this study are:

- MACE (CV death, MI, or stroke) and other specific CV events (eg, heart failure leading to hospitalization)
- Severe hypoglycemia (see [Section 10.6.1](#))
- Genital mycotic infections (to include vulvovaginal candidiasis in females and candidal balanitis in males)
- Urinary tract infections
- Clinically relevant volume depletion and events related/possibly related to volume depletion
- Diarrhea
- Pancreatitis
- Bone fractures
- Venous thrombotic events, to include deep venous thrombosis and thromboembolism (to include pulmonary embolism)
- Diabetic ketoacidosis
- Renal events, to include 50% decline in eGFR, end stage kidney disease, renal death
- Malignancies of special interest (breast, bladder, renal cell, Leydig cell, pancreatic, prostate, and thyroid cancer)
- Adverse events leading to amputation.

#### 10.4.2 General guidelines for reporting adverse events

- All AEs, regardless of seriousness or relationship to IMP/NIMP, spanning from the signature of the ICF until the end of the study as defined by the protocol for that patient, are to be recorded on the corresponding page(s) or screen(s) of the e-CRF.
- Whenever possible, diagnosis or single syndrome should be reported instead of symptoms. The Investigator should specify the date of onset, intensity, action taken with respect to IMP, corrective treatment/therapy given, additional investigations performed, outcome, and his/her opinion as to whether there is a reasonable possibility that the AE was caused by the IMP or by the study procedure(s).
- In this study, the use of concomitant medications including antidiabetic medications may make it difficult to assess the causal relationship, particularly for hypoglycemia. Global Safety Officer with input from other appropriate study team members will determine the causal relationship when it is not clearly provided by the Investigator.
- The Investigator should take appropriate measures to follow all AEs until clinical recovery is complete and laboratory results have returned to normal, or until progression has been stabilized, or until death, in order to ensure the safety of the patients. This may imply that observations will continue beyond the last planned visit per protocol, and that additional investigations may be requested by the monitoring team up to as noticed by the Sponsor.
- When treatment is prematurely discontinued, the patient's observations will continue until the end of the study as defined by the protocol for that patient.
- Laboratory, vital signs or ECG abnormalities are to be recorded as AEs if they are medically relevant based on the investigator's medical judgment, eg:
  - Symptomatic and/or
  - Requiring either corrective treatment or consultation and/or
  - Leading to IMP discontinuation or modification of dosing and/or
  - Fulfilling a seriousness criterion and/or
  - Defined as an AESI or EOSI.

#### 10.4.3 Instructions for reporting serious adverse events

In the case of occurrence of an SAE, the Investigator or any designees must immediately:

- ENTER (within 24 hours) the information related to the SAE in the appropriate screens of the e-CRF; the system will automatically send the notification to the Monitoring team and Pharmacovigilance after approval of the Investigator within the e-CRF.
- SEND (preferably by fax or e-mail) a photocopy of all examinations carried out and the dates on which these examinations were performed, to the representative of the monitoring team whose name, fax number, and e-mail address appear on the clinical trial protocol. Care should be taken to ensure that the patient's identity is protected and the patient's identifiers in the clinical trial are properly mentioned on any copy of a source document provided to the Sponsor. For laboratory results, include the laboratory normal ranges.

- All further data updates should be recorded in the e-CRF as appropriate, and further documentation as well as additional information (for laboratory data, concomitant medications, patient status, etc) should be sent (by fax or e-mail) to the monitoring team within 24 hours of knowledge of the SAE. In addition, every effort should be made to further document any SAE that is fatal or life-threatening within a week (7 days) of the initial notification.
- A back-up plan (using a paper case report form [CRF] process) is available and should be used when the e-CRF system does not work.

Any SAE brought to the attention of the Investigator at any time after the end of the study for the patient and considered by him/her to be caused by the IMP with a reasonable possibility, should be reported to the monitoring team.

#### **10.4.4 Guidelines for reporting adverse events of special interest**

For AESIs, the Sponsor must be informed immediately (ie, within 24 hours), as per SAE notification guidelines described in [Section 10.4.3](#), even if not fulfilling a seriousness criterion, using the corresponding pages of the CRF (to be sent) or screens in the e-CRF.

#### **10.4.5 Guidelines for reporting events of special interest**

If an EOSI fulfills the criteria of an SAE, reporting should be performed according to the instructions for reporting of SAEs (see [Section 10.4.3](#)). Otherwise, reporting should follow the instructions for an AE (see [Section 10.4.2](#)).

#### **10.4.6 Guidelines for management of specific laboratory abnormalities**

Decision trees for the management of certain laboratory abnormalities by Sanofi are provided in [Appendix D](#).

The following laboratory abnormalities should be monitored, documented, and managed according to the related flow chart in protocol appendices:

- Neutropenia
- Thrombocytopenia
- Increase in ALT
- Acute renal insufficiency
- Suspicion of rhabdomyolysis

## 10.5 OBLIGATIONS OF THE SPONSOR

During the course of the study, the Sponsor will report in an expedited manner:

- All SAEs that are both unexpected and at least reasonably related to the IMP (SUSAR) to the regulatory authorities, independent ethics committee (IECs)/institutional review boards (IRBs) as appropriate and to the Investigators;
- All SAEs that are expected and at least reasonably related to the IMPs to the regulatory authorities, according to local regulations;
- The following AESIs to those regulatory authorities who require such reporting:
  - Pregnancy
  - Symptomatic overdose
  - ALT increase >3 times ULN

Adverse events that are considered expected will be specified by the reference safety information provided in the current IB.

If required, unblinding of SUSARs will be the responsibility of the Sponsor.

The Sponsor will report all safety observations made during the conduct of the trial in the CSR.

## 10.6 SAFETY INSTRUCTIONS

[figure not shown]
### 10.6.1 Hypoglycemia

During the study, patients are instructed to document any hypoglycemic episodes in their study diary. The hypoglycemia will be reported in the specific e-CRF page with onset date and time, symptoms and/or signs, the SMBG value if available, and the treatment. If the event fulfills SAE criteria, hypoglycemia will also be reported as an SAE.

Hypoglycemia is categorized according to the American Diabetes Association workgroup on hypoglycemia classification (20, 21) and summarized in [Figure 1](#).

In addition to the threshold of less than or equal to 70 mg/dL (3.9 mmol/L), hypoglycemia episodes with a plasma glucose of <54 mg/dL (3.0 mmol/L) will be analyzed separately.

**Figure 1 - Hypoglycemia classification in Study EFC15166**

\*The patient is not able to treat her/himself because of the acute neurological impairment and requires another person to actively administer sugar, glucagon or intravenous glucose

PG = plasma glucose; SAE = serious adverse event

### Severe hypoglycemia

Severe hypoglycemia is an event requiring assistance of another person to actively administer carbohydrate, glucagon, intravenous glucose or other resuscitative actions. These episodes may be associated with sufficient neuroglycopenia to induce seizure, unconsciousness or coma. Self-monitored plasma glucose values may not be available, but neurological recovery attributable to the restoration of plasma glucose to normal is considered sufficient evidence that the event was induced by a low plasma glucose concentration.

**Note:** “Requiring assistance of another person” means that the patient could not help himself or herself to treat the hypoglycemia. Assisting a patient out of kindness, when assistance is not required, should not be considered a “requires assistance” incident.

Any hypoglycemic event which leads to unconsciousness, coma, or seizure should also be reported as an SAE.

### Documented symptomatic hypoglycemia

Documented symptomatic hypoglycemia is an event during which typical symptoms of hypoglycemia accompanied by a measured plasma glucose concentration of  $\leq 3.9$  mmol/L ( $\leq 70$  mg/dL).

Clinical symptoms that are considered to result from a hypoglycemic episode include, increased sweating, nervousness, asthenia/weakness, tremor, dizziness, increased appetite, palpitations, headache, sleep disorder, confusion, seizures, unconsciousness, or coma.

### **Asymptomatic hypoglycemia**

Asymptomatic hypoglycemia is an event not accompanied by typical symptoms of hypoglycemia but with a measured plasma glucose concentration  $\leq 3.9$  mmol/L ( $\leq 70$  mg/dL).

**Note:** low plasma glucose values without symptoms or signs should not be reported more than once within 30 minutes. Repeated low glucose values within a short period could be due to malfunction of the device, error testing or following up a low glucose reading. The Investigator should try not to document false low SMBG values or redundant low glucose values as asymptomatic hypoglycemic events. Further clarification with the patients is needed.

### **Probable symptomatic hypoglycemia**

Probable symptomatic hypoglycemia is an event during which symptoms of hypoglycemia are not accompanied by a plasma glucose determination, (but that was presumably caused by a plasma glucose concentration  $\leq 3.9$  mmol/L [ $\leq 70$  mg/dL]), ie, symptoms treated with oral carbohydrate **without** a test of plasma glucose.

### **Relative hypoglycemia**

Relative hypoglycemia, recently termed “pseudo-hypoglycemia” (22), is an event during which the patient reports typical symptoms of hypoglycemia, and interprets the symptoms as indicative of hypoglycemia, but with a measured plasma glucose concentration  $> 3.9$  mmol/L ( $> 70$  mg/dL).

## **10.6.2 Deterioration of renal function**

Patients will be monitored throughout the double-blind Treatment Period for signs of deterioration in renal function (eg, decrease in eGFR or increase in creatinine as defined below) as well as other routine clinical and laboratory findings (see Study Flowchart, [Section 1.2](#)). If at any visit after randomization up to Week 8 there is a rise in creatinine level (ie,  $> 50\%$  increase from baseline level, where baseline level is defined as the mean of creatinine values obtained at Screening and Randomization) or if at any visit after Week 8 there is a rise of  $> 50\%$  above the mean of creatinine values from last 2 visits, the Investigator should ensure that no reasonable explanation exists for creatinine increase and in particular the following causes:

- Medications that increase creatinine
- Decrease in cardiac output
- Obstructive uropathy
- Urinary tract infection
- Volume depletion

If addressing these causes does not reduce the creatinine level below the above stated threshold, the IMP will be stopped for 2 weeks. The dose will be handling according to the renal function assessed by the creatinine measurement throughout the study and as detailed in [Section 10.3.1](#).

If the creatinine dose not return to below the threshold, then the IMP will be permanently discontinued but the patient will be asked to continue attending all study visits.

## **10.7 ADVERSE EVENTS MONITORING**

All events will be managed and reported in compliance with all applicable regulations, and included in the final CSR.

## 11 STATISTICAL CONSIDERATIONS

### 11.1 DETERMINATION OF SAMPLE SIZE

The sample size/power calculations were performed based on the primary endpoint. Assuming a common standard deviation of 1.2% and using a 2-sided test at a 0.05  $\alpha$ -level, 92 patients in each group will provide at least 80% power to detect a treatment difference of 0.5% in mean HbA1c change from Baseline to Week 26 between sotagliflozin 400 mg and placebo.

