--	---

	
 
• Reversible causes of renal failure such as obstruction
 
• Pregnancy or breastfeeding
 
• Women of childbearing potential (WOCBP) not willing to use highly effective method(s) of birth control during the study treatment period and the follow-up period, or who are unwilling or unable to be tested for pregnancy (see Appendix A), during the study
 
• Mean of 3 separate blood pressure (BP) measurements >180 mmHg (SBP) or >100 mmHg (diastolic blood pressure [DBP])
 
• Systolic BP <120 mmHg or DBP <60 mmHg if the patient is on hypertensive medications
 
• History of prior gastric surgery including history of gastric banding or inflammatory bowel disease within 3 years prior to the Screening Visit
 
• Aspartate aminotransferase (AST) and/or alanine aminotransferase (ALT) >3 times the upper limit of the normal laboratory range (ULN)
 
• Total bilirubin: >1.5 times the ULN (except in the case of Gilbert's Syndrome)
 
• Patients unwilling or unable to perform self-monitoring of blood glucose (SMBG), complete the patient diary or comply with study visits and other study procedures as required per protocol
 

Total expected number of patients:	276 randomized patients
Expected number of sites:	Approximately 110
STUDY TREATMENTS	
Investigational medicinal products	
 
• Sotagliflozin 200 mg, given as 2 tablets: 1 sotagliflozin 200-mg tablet and 1 placebo tablet (identical to sotagliflozin in appearance), once daily before the first meal of the day;
 
• Sotagliflozin 400 mg, given as 2 sotagliflozin 200-mg tablets, once daily before the first meal of the day;
 
• Placebo, given as 2 placebo tablets (identical to sotagliflozin in appearance), once daily before the first meal of the day.
 

Formulation:	Tablet
Route of administration:	Oral
Dose regimen:	Once daily

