1.3 DETERMINATION OF SAMPLE SIZE

The sample size/power calculations were performed based on the primary endpoint. Assuming a common standard deviation of 1.2% and using a 2-sided test at a 0.05 α -level, 92 patients in each group will provide 80% power to detect a treatment difference of 0.5% in mean HbA1c change from Baseline to Week 26 between sotagliflozin 400 mg and placebo.

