2.4.4.1 Analysis of primary efficacy endpoint(s)

The statistical tests will be two-sided tests at a nominal 5% significance level.

Primary analysis

The primary efficacy endpoint of change in HbA1c from baseline to Week 26 will be analyzed by an ANCOVA model using HbA1c values measured at baseline and Week 26 (observed or imputed). The missing data at endpoint will be imputed by multiple imputation (MI) methods in 2 parts as detailed below. To be concise, the following texts related to imputation are generalized to accommodate primary as well as continuous secondary efficacy endpoints.

1. Missing endpoint data for patients who prematurely discontinue the IMP before the Week 26 (or Week 12 for SBP) visit will be imputed using a model built separately in each treatment group and estimated from the patients in the same treatment group who prematurely discontinue the IMP before the Week 26 (or Week 12 for SBP) visit but have the measurement for the endpoint (retrieved dropouts). Considering that the number of patients in each treatment group who discontinue the IMP but have the measurement for the endpoint is expected to be small, a simple imputation model based on regression will be used with baseline measurement included as the predictor. Each treatment group will have their own imputation model.
2. Missing endpoint data for all patients who stay on the IMP until the Week 26 (or Week 12 for SBP) visit, including those in the sotagliflozin groups, will be imputed separately. The wash-out imputation method will be used, where missing endpoint data in the sotagliflozin groups, as well as in the placebo group are imputed from a model estimated from patients in the placebo group who stay on the IMP until the Week 26 (or Week 12 for SBP) visit and have the endpoint data available. The imputation model will include the randomization strata and the corresponding baseline value. Missing data will be imputed using the regression method.

An alternative (back-up) imputation method will be used if the number of patients who prematurely discontinue the IMP before the Week 26 (or Week 12 for SBP) visit but have the measurement for the endpoint is <5 in any treatment groups (ie, not sufficient retrieved dropouts to support the imputation method described above). This criterion will be assessed for each primary or continuous secondary efficacy endpoint separately.

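### The stated power of at least 80% is a complete-data figure: on the stated inputs, 276 randomized (3 x 92) leaves no allowance for missing Week 26 HbA1c

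*Protocol*

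**What the plan says.** Protocol 11.1 gives the inputs as "Assuming a common standard deviation of 1.2"%, "using a 2-sided test at a 0.05" level, and a sample sized "to detect a treatment difference of 0.5% in mean HbA1c change from Baseline to Week 26" between sotagliflozin 400 mg and placebo. It concludes that "92 patients in each group will provide at least 80% power". SAP 1.3 gives the same inputs without the words at least: "92 patients in each group will provide 80% power to detect a treatment difference of 0.5"%. The synopsis plans "276 randomized patients", allocated 1:1:1.

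Neither sample-size section states a dropout or missing-data rate, the source of 0.5% and 1.2%, or whether 1.2% is the SD of the raw change or the residual SD after ANCOVA.

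The analysis sections do provide for missing values:

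- Protocol 11.4.2.1 imputes missing sotagliflozin values as though the patient had been on placebo.
- SAP 2.4.4.1 replaces this with two steps. Patients who stopped IMP are imputed from patients in the same arm who stopped but still have a Week 26 value (retrieved dropouts). For patients still on IMP, "missing endpoint data in the sotagliflozin groups, as well as in the placebo group are imputed from a model" fitted to placebo patients (wash-out).
- The SAP back-up is control-based copy reference, used if any arm has fewer than 5 retrieved dropouts.

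**The concern.** The number in the power calculation and the number randomized are the same, 92 per arm. That is consistent only if every randomized patient contributes a Week 26 HbA1c. The plan does not expect this. Patients who decline site visits are followed by telephone (Protocol 6.1.2), which yields no HbA1c. Permanent discontinuation is foreseen for unrecovered creatinine rises and for renal replacement therapy (Protocol 10.3.3). SAP 2.4.4.1 expects few retrieved dropouts.

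The primary comparison opens the whole testing hierarchy (Protocol 11.4.2.4, SAP 2.4.4.4). If it is not significant, no secondary endpoint can be claimed. A reader judging that risk needs the power of the specified analysis, not of one without missing data.

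**Working it through.** **Inputs from the documents:** difference 0.5%, SD 1.2%, two-sided alpha 0.05, 92 per arm (Protocol 11.1, SAP 1.3); 276 randomized, and 276/3 = 92. **Assumed:** missing fraction m at Week 26, equal in both arms.

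**1. The plan's figure.** Two-sample t-test with noncentrality 0.5 / (1.2 x sqrt(2/n)). At n = 92 this is 0.5/0.1769 = 2.826 on 182 df, giving power 80.3%. At n = 91 it is 79.8%. So 92 is the smallest size per arm that reaches 80%. The normal approximation gives 80.7% at 92 and first reaches 80% at 91, so the slack is at most one patient per arm. The smallest difference with 80% power at n = 92 is 0.496% (normal approximation).

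**2. Loss of information only.** The effect stays at 0.5% and n becomes 92(1 - m).

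**3. Missing active-arm values carry no drug effect.** The expected difference becomes 0.5(1 - m), with n kept at 92. For m = 0.10 the noncentrality is 0.45/0.1769 = 2.543.

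| Missing (assumed) | Step 2 | Step 3 |
|---|---|---|
| 0% | 80.3% | 80.3% |
| 1% | 79.9% | 79.5% |
| 2% | 79.5% | 78.7% |
| 5% | 78.2% | 76.1% |
| 10% | 76.0% | 71.6% |
| 20% | 70.9% | 61.4% |

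**4. Closer to the planned methods.** These are simulations with ANCOVA and Rubin's rules at residual SD 1.2.

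- Placebo wash-out for all missing values: about 76%, 69% and 53% at 5%, 10% and 20% missing. Step 3 is therefore slightly optimistic for this method at the higher rates.
- Copy reference with one interim visit (assumed correlation 0.6): about 78%, 76% and 71%. It loses less because earlier on-treatment values carry part of the effect forward.
- SAP retrieved-dropout step, with 13 of 92 per arm assumed to stop IMP and 8 of them retrieved (5/92, about 5% missing): about 72% if 0.5% is the overall effect including patients who stop, and about 59% if 0.5% is an on-drug effect lost on stopping. The second figure includes dilution from observed off-drug values, not only from missing ones.

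**5. If 1.2% is a raw SD.** A residual SD of 1.1 corresponds to a multiple correlation of sqrt(1 - (1.1/1.2)^2) = 0.40 between the change and the model terms. Step 3 power is then 83.0%, 78.8% and 68.9% at 5%, 10% and 20% missing, and step 2 power is 84.8%, 82.8% and 78.2%. At residual SD 1.0, step 3 gives 85.9% at 10% and 77.0% at 20%.

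**The case against.** The strongest case against has four parts.

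- **The arithmetic is right.** The stated power reproduces. This stands: the fault is an unstated complete-data assumption, not a miscalculation.
- **The SAP's preferred method is not placebo-based for patients who stop IMP.** This also stands. A reader might infer that placebo-based imputation causes the shortfall and that 76%, 72% and 61% are this trial's power. The documents do not support that. Those figures approximate the method in Protocol 11.4.2.1 and the wash-out step for patients still on IMP, and match no planned analysis exactly. The shortfall does not depend on them, because loss of information alone gives 78.2% at 5% missing.
- **The inputs may hide a margin.** The ANCOVA adjusts for baseline HbA1c, strata and country, so a raw SD of 1.2% could shrink enough to restore 80% at modest missing rates. Likewise 0.5% may already be a treatment-policy effect, and diluting it again would then count the loss twice. Both are possible and neither is stated. In the second case the step 2 loss remains.
- **Missing values may be few.** Values after IMP discontinuation or rescue count, patients who stop are asked to keep attending, and unscheduled values from Days 154 to 227 can stand in for Week 26 (SAP 2.5.4). This limits the rate, and nothing in the documents supports 20% in particular. At residual SD 1.2%, however, 1-2% is enough to pass below 80%.

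The practical stakes are also limited: SAP 1.6 reports that the first-step analysis has been done for top-line results.

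**Conclusion.** The point holds as a statement about the stated inputs. With residual SD 1.2%, difference 0.5% and two-sided 0.05, 92 per arm just reaches 80% with complete data, and the design has no reserve. Power is about 78%, 76% and 71% at 5%, 10% and 20% missing with no dilution. It is about 76%, 72% and 61% or lower if missing active-arm values carry no drug effect, with copy reference losing less than full wash-out. The missing rates are assumptions.

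It would be too strong to say that 80% power requires all 92 patients per arm to have a Week 26 value under every reading of the inputs. A raw SD of 1.2% that the ANCOVA brings down to 1.1% would leave 83% at 5% missing even with full dilution. Nor do the documents show that the trial is underpowered by a known amount. They show a power claim that omits a condition it depends on.

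**What to change.** In Protocol 11.1 and SAP 1.3:

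1. Replace the claim of 80% or more with 80.3% given complete Week 26 data.
2. Give the power over a stated range of missing rates under SAP 2.4.4.1: retrieved dropout plus wash-out, and separately the copy-reference back-up. State the assumed numbers who stop IMP and who are retrieved.
3. State whether 1.2% is a raw or an ANCOVA-residual SD.
4. State whether 0.5% is the treatment-policy effect, already diluted by patients who stop, or an on-drug effect.

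The figures in the working are illustrations and should not be copied in as the trial's power; the second item needs a short simulation under the sponsor's own assumptions. No patients are added and no test, alpha level or estimate changes. The cost is that simulation, an edit to two short sections, and a slightly less favourable stated power.
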